- Measurement of cervical and thoracic axial range of motion using video motion capture technology
- Field of view testing
- 10s grip and release test, 10s step test, Tandem Gait (heel-to-toe) walk*
- Testing of driving performance using a customized driving simulator set-up
- All other procedures are standard of care for all investigators involved

- E. ***These tests tend to be done as part of standard of care identifying myelopathy patients, but in the case it is not performed as standard of care we will perform the tests as a research procedure. Only clinical research staff or non-clinical staff trained to perform the tests will perform the tests. For non-clinical staff who received training, we will still ensure a clinician is in close proximity if help is needed while doing the tests.**

INCLUSION CRITERIA

- *Study Subjects:*
 - Age between 18 and 80 years
 - Indicated for elective cervical spine surgery (including ACDF [single or multi-level], posterior cervical laminectomy and fusion, posterior cervical laminoplasty, posterior cervical foraminotomy, cervical disc replacement) after failing at least 6 weeks of non-operative treatment modalities
 - Valid driving license
 - Regular use of a vehicle
 - Signed consent form
- *Control Subjects:*
 - Age between 18 and 80 years
 - No pre-existing or recent injuries to neck, torso, back
 - No neurologic or systemic debilitating conditions
 - Valid driving license
 - Regular use of a vehicle
 - Signed consent form

F. EXCLUSION CRITERIA

- Significant visual impairment
- Significant debilitating neurological condition with loss of function of one or more extremities
- Recent extremity surgery
- Recent eye surgery
- Previous history of motion sickness, vertigo in simulated settings
- Recent history of chemical or narcotic dependency

G. VULNERABLE POPULATION

Students and faculty of NYU School of Medicine and NYU Langone Medical Center will be recruited as potential control subjects and will be eligible to participate in the study. Students and faculty can voluntarily participate in this study without coercion. The Principal Investigator, Sub-Investigators, and research staff will ensure there are additional safeguards for these subjects. They will

NCT02782923

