Visual inspection of the rearview and side mirrors and the blind spot using appropriate eye-head movements is generally needed before taking the decision to change lanes (35). The driving scenario will include 20 events for which the driver would require evaluation of blind spots prior to lane changes. Based on data published by the U.S. Department of Transportation, National Highway Traffic Safety Administration (Figure 3) from experimental analysis of blind spot position for 75 vehicles, four multi-colored LED lights (AOMETech, Guangzhou, China) will be placed in constant locations relative to the subject to simulate the blind spot (36). The lights have a control feature, which allows the operator to change the color remotely. Prior to testing, subjects will be instructed that a “green” light will signify that there are no vehicles in the blind spot and a “red” light will signify that there is a vehicle in the blind spot (See Figure 1 for depiction). Prior to beginning the trials, patients will be instructed to check appropriate blind spots prior to all lane-changing events. If a subject changes lanes without checking the appropriate blind spot or changes lanes when a vehicle appears in a particular blind spot, an unsafe driving event (UDE) will be recorded. The total amount of UDE occurrences will be recorded for each patient in each trial. The appearance of vehicles in each blind spot will remain constant for all patients in each particular phase of testing (i.e. pre-operative) however, locations will be randomized across each subsequent trial (i.e. 2, 6 and 12-weeks post-operatively) to prevent learning bias.

[figure not shown]
NCT02782923

Figure 3: Actual vehicle representation of decreased visibility (Mazzae, NHTSA 2009)

Location 1 is located on the left, 5 feet lateral from the subject. (L1)

Location 2 is located on the left, 5 feet lateral and 10 feet posterior from the subject. (L2)

Location 3 is located on the right, 5 feet lateral from the subject. (R1)

Location 4 is located on the right, 5 feet lateral and 10 feet posterior from the subject. (R2)

Measurement of Driving Performance

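### Blind-spot occupancy is signalled by red versus green with no stated colour-vision check, so a misread light can be scored as an unsafe driving event (minor)

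*Protocol*

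**What the plan says.** All of the task is in Protocol IV.N, Lane Changes and Blind Spot Detection. Four LEDs stand in fixed places around the subject, and only their colour changes: "The lights have a control feature, which allows the operator to change the color remotely". The code is that "a “green” light will signify that there are no vehicles in the blind spot and a “red” light will signify" an occupied blind spot.

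A UDE is scored in two ways:
- Failure to check: "If a subject changes lanes without checking the appropriate blind spot".
- Moving into an occupied spot: the subject "changes lanes when a vehicle appears in a particular blind spot, an unsafe driving event (UDE) will be recorded".

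The two are then added together: "The total amount of UDE occurrences will be recorded for each patient in each trial". On the number of opportunities: "The driving scenario will include 20 events for which the driver would require evaluation of blind spots prior to lane changes". How many of these show red is not stated. Between phases, "locations will be randomized across each subsequent trial", while the pattern is the same for all patients within a phase.

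Vision is addressed in four places. IV.F excludes "Significant visual impairment", without defining it, and also recent eye surgery. IV.N, Demographic Information and Questionnaires, records ocular history, with no stated use in eligibility or analysis. IV.N, Clinical Evaluation, adds a field-of-view evaluation before each trial. Colour vision is not named in any of these or in Table 1 (IV.P). The training circuit in IV.N, Driving Simulator, has no stated check that the subject can tell the two lights apart.

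**The concern.** The blind-spot task is there to show whether restricted rotation of the neck or torso stops a driver from seeing what is beside and behind. A driver who rotates fully, looks at the correct light and takes red for green has no such restriction, yet changing lanes then counts as a UDE. Because the two components are pooled, that driver cannot be told apart in the recorded total from one who could not turn. Hesitation over the colour could also lengthen the time to initiate a lane change, which is a separate outcome in Table 1.

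At stake is the validity of one named driving-performance measure and, to a lesser degree, of that timing outcome. Collisions, centreline crossings and off-road excursions do not depend on the lights.

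**Working it through.** The Protocol gives no figure on this point to reproduce. The check has two parts: what the text allows, and how large the effect could be.

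**What the text allows.** With fixed light positions and only the colour changing, colour is the sole occupancy cue described. The failure-to-check component does not use colour; the occupied-spot component does. Reading green as red adds no UDE under the written definition, so the error inflates the count in one direction only.

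**Inputs from the Protocol.** 20 blind-spot events per drive; 30 patients in each of 5 surgical groups (150); 40 controls.

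**Inputs assumed, because the Protocol gives none.** Prevalence of relevant colour deficiency p = 0.5% to 8%; probability of misreading a red light q = 10% to 50%; red events per drive k = 5 to 15.

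**Subjects affected.** Expected number = n × p; chance of at least one = 1 − (1 − p)^n.

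| Set | Expected number | Chance of at least one |
|---|---|---|
| Group of 30 | 0.15 to 2.4 | 14% to 92% |
| 150 surgical patients | 0.75 to 12 | 53% to nearly 100% |
| 40 controls | 0.2 to 3.2 | 18% to 96% |

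**Spurious UDEs per affected subject** = k × q: from 5 × 0.10 = 0.5 to 15 × 0.50 = 7.5, out of 20 events.

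**Expected shift in a group mean** = p × k × q: from 0.005 × 0.5 = 0.0025 to 0.08 × 7.5 = 0.6 UDE.

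**Added between-subject variance** = p(1 − p)(kq)² + p·k·q(1 − q): from about 0.003 to 4.44. The middle of the range is modest: at p = 2%, k = 10, q = 10% it is 0.038.

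**Shift in the within-patient change** = p × q × (difference in k between phases), assuming that the deficiency and the misreading rate are stable over follow-up:
- Same number of red events in both phases: 0.
- Difference of 5 red events, q = 50%: 0.005 × 0.5 × 5 = 0.013 to 0.08 × 0.5 × 5 = 0.2 UDE.

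**Noise left in the change even with equal red counts.** At k = 10 and q = 50%, each drive of an affected patient carries binomial variance 10 × 0.5 × 0.5 = 2.5, so the pre/post difference carries 2 × 2.5 = 5. With one affected patient in 30, that averages 5/30 = 0.17 over the group.

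**The case against.** The strongest reply is that both study aims in IV.N compare each patient with his or her own pre-operative drive. A stable deficiency is then present at both ends and its expected effect drops out. This stands, provided the number of red events is equal across phases. The Protocol randomizes locations between phases but says nothing about the count, and misreading noise remains even when the counts match.

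Three further replies also stand in part:
- The exclusion for visual impairment is undefined and might be applied to colour deficiency, and ocular history might reveal a known case. Neither use is stated. A reader might infer that a licensed colour-deficient driver is certain to pass the vision criteria; the text settles this neither way.
- LED hue, brightness and misreading rate are not given, and the Protocol refers to a figure for the depiction of the signals that is not available here. A reader might infer that colour-deficient drivers will score unsafe events. The text supports only that they can.
- Nothing in the Protocol ties colour vision to study group. A reader might infer that the comparison with controls is biased. No bias is expected there, only chance imbalance, although volunteers are tested in one sitting and so have no baseline of their own to cancel it.

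It would also be tempting to quote a single large variance inflation. Such a figure comes from fixing a high misreading rate and looking at one time point; it does not carry over to the change from baseline.

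**Conclusion.** The point holds as a minor gap in measurement validity. Followed exactly, the Protocol can count a misread colour as unsafe driving unrelated to neck function. It has no step to detect this, and its pooled total does not allow it to be separated afterwards.

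The effect is confined to the occupied-spot component of the UDE and possibly to the time to initiate a lane change. It can be large for one affected driver (0.5 to 7.5 events) but is usually small for a group mean (0.0025 to 0.6 UDE). For the within-patient aims it is close to nil in expectation if the red count is held constant. What remains is extra noise and possible chance imbalance in comparisons between procedures and with controls.

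These sizes rest wholly on the assumed prevalence, misreading rate and red count, and the cancellation rests on colour vision being stable over follow-up. The documents do not support the wider reading that UDE results as a whole are invalid or that either aim is compromised.

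**What to change.** 1. Use a signal pair that does not rely on red-green discrimination, for example blue versus amber, or steady versus flashing. The LEDs are already multi-coloured and their colour is set remotely; whether they can flash is not stated and would need checking.
2. At the existing training circuit, have each subject look straight at a light and name both signals, and record the result.
3. Record for each of the 20 events whether it was a failure to check, a lane change into an occupied spot, or both. The operator must already judge this to score a UDE.
4. Fix the number of vehicle-present events and hold it equal across phases, still randomizing their locations.

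If drives have already been recorded, keep red/green for consistency and add the naming check. Then run a sensitivity analysis of the colour-dependent component without the subjects who fail the check. They should stay in the main UDE analysis, because patients serve as their own controls and the failure-to-check component is unaffected.

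The cost is a changed LED setting, one line of instruction and a brief check at the training drive.

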6. Myelopathy patients who do not undergo surgery (N=20)
7. Control group (C); n=40

*Patients who have myelopathy undergoing surgery fall under groups 1 -5 and have not been grouped differently given they belong first to the above groups before being sub-identified as the myelopathy group

The first aim of this study is to elucidate the time interval in the post-operative period in which there is the largest decline in driving performance. The second aim of this study is to evaluate the post-operative time interval at which patients' return to baseline driving performance. We will address all clinical questions by comparing the outcomes measures of driving performance pre-operatively and at three subsequent post-operative time points: 2 weeks (PO₂), at 6 weeks (PO₆) and at 12 weeks (PO₁₂). We will also use the NDI, PROMIS and NRS scores collected at each interval to elucidate whether these clinical questionnaires serve a predictive role in evaluating driving performance. This information will also be compared to control data obtained from healthy

NCT02782923

volunteers. The driving-simulator experimental set-up will consist of the subject sitting in front of the driving simulator with three screens allowing for an 180° field-of-view with a camera positioned overhead; the subject will have markers placed over shoulders and head to allow for motion-capture analysis with objects placed at various locations to simulate blind spots. Figure 1 summarizes the experimental set-up. Table 1 summarizes all outcome measures and data collection timeline.

[figure not shown]

Figure 1: Experimental Set-Up

Driving Simulator

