subjects in simulated real-world driving conditions. Car and steering responses will be recorded with STISIM software. Data will be collected for specific events during the programmed driving scenario. Each subject will be allowed a single training circuit to familiarize to the simulator prior to any data collection. Patients will undergo testing using a simulated driving circuit (SDC) lasting approximately fifteen minutes. The SDC is designed to represent a combination of suburban, highway and residential driving environments. The course will recreate standard turns, traffic intersections, pedestrian crosswalks, lane changes and several hazardous conditions routinely encountered during driving situations. Patients will be instructed to stay below the indicated speed limit. In the event that subjects exceeded this limit, a computer-generated auditory warning will be issued. There will be pre-programmed prompts during the circuit to indicate to the driver to perform specific maneuvers (change lanes, turn at intersection, come to full stop). Subjects will be informed that the simulator could make them feel uncomfortable and they will be instructed to inform the experimenter if this happens, at which point, the scenario will be stopped immediately.

Measurement of Cervical Rotation

Cervical axial rotation will be recorded using an overhead camera(Canon, Melville, NY) positioned over the simulator set-up as graphically depicted in Figure 2. Four video markers will be placed on the subjects head, 2 markers will be placed on the acromio-clavicular joint and 4 markers will be placed on the ground to serve as reference points as depicted in Figure 1. Video motion analysis software (Dartfish, Atlanta, GA) will be used to measure cervical and thoracic rotation using the static ground video markers as a reference. Prior to beginning each trial, painless maximal axial rotation of the neck and torso will be collected by having the patient sit in the simulator and follow these prompts:

1. *While keeping your torso still, please rotate your head as far right as you can, stopping at the point of discomfort. Now repeat, by rotating your head as far left as you can, stopping at the point of discomfort. (maximal axial rotation of neck)*

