2. *While keeping your neck still, please rotate your body as far right as you can, stopping at the point of discomfort. Now repeat, by rotating your body as far left as you can, stopping at the point of discomfort. (maximal axial rotation of torso)*
3. *You can now rotate both your body and neck as far right as you can, stopping at the point of discomfort. Now repeat, by rotating your body and neck as far left as you can, stopping at the point of discomfort. (maximal axial rotation)*

The amount of rotation during each specified lane change or turning event during each testing interval will be collected and recorded. Additionally, the time required to achieve maximal rotation and time required prior to initiating and completing a lane change will be collected. Finally, the average and maximal amount of axial range of motion will be collected over each testing interval and compared.

NCT02782923

[figure not shown]

Figure 2: Lateral view of experimental set-up

Lane Changes and Blind Spot Detection

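### One blind-spot layout per visit, redrawn between visits with no balancing rule, confounds layout with post-operative time in the unsafe-driving-event total

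*Protocol*

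**What the plan says.** Section IV.N of the Protocol, under Lane Changes and Blind Spot Detection, sets the rule in one sentence. Its first half reads "The appearance of vehicles in each blind spot will remain constant for all patients in each particular phase of testing". Its second half adds that "locations will be randomized across each subsequent trial (i.e. 2, 6 and 12-weeks post-operatively) to prevent learning bias".

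The same subsection gives the rest of the set-up:

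- Number of events: "The driving scenario will include 20 events for which the driver would require evaluation of blind spots prior to lane changes".
- Four light positions. L1 and R1 are 5 feet to the side of the subject; L2 and R2 are 5 feet to the side and 10 feet behind.
- A UDE is scored if the subject does not check the appropriate blind spot. It is also scored if the subject "changes lanes when a vehicle appears in a particular blind spot, an unsafe driving event (UDE) will be recorded".
- The only UDE summary named: "The total amount of UDE occurrences will be recorded for each patient in each trial".

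Earlier in section IV.N, the first aim is to "elucidate the time interval in the post-operative period in which there is the largest decline in driving performance". The second is to find when patients are back at baseline. Both are to be answered by comparing pre-operative performance with 2, 6 and 12 weeks.

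**The concern.** If all patients share a layout at a visit and the layout changes at the next, any difference in layout difficulty is added to the visit effect. A layout that happens to be harder at 2 weeks looks like a post-operative decline; an easier one at 12 weeks looks like recovery. The shift is common to everyone at that visit, so recruiting more patients makes it look more certain and does not average it out.

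Equal difficulty cannot be presumed. The rear positions need far more rotation to see than the lateral ones, and the Background (section II) itself treats neck and torso rotation as critical for changing lanes and expects it to fall after cervical surgery.

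Nothing else in the design separates the two effects. Healthy controls are tested in one phase only (section IV.C) and are given no role in estimating a layout effect. The non-surgical myelopathy group (N=20) has no stated visit schedule.

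This is a rule for collecting data. An analysis plan could repair only part of it afterwards.

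**Working it through.** **1. Structure (no assumed rates).** Model a patient's UDE total with an intercept, 3 visit terms and 3 layout terms, 7 columns in all. With one layout per visit the layout columns equal the visit columns, and the matrix has rank 4. With four layouts rotated over patients by a Latin square the rank is 7. As written, no within-group analysis of the total can separate time from layout.

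**2. Geometry.** L1/R1 lie at 90° from straight ahead. L2/R2 lie at 180° − atan(5/10) = 153.4°.

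**3. Size of the front/rear part.** The Protocol gives no miss rates, no SD and no number of occupied events, so there is no stated figure to reproduce and every input here is an assumption:

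- K = 10 of the 20 events show a vehicle, each at a rear position with probability 0.5, drawn independently per visit.
- δ is the extra UDE probability when the vehicle is at the rear rather than the lateral position.
- The SD of within-patient change in the UDE total is 2, with no true change.
- Test: two-sided 5% paired t, one pre- versus post-operative contrast.

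Let D be the difference in rear counts between two layouts. Var(D) = 2 × 10 × 0.25 = 5, so SD(D) = 2.24. The spurious shift is δ × D; at δ = 0.20 its SD is 0.20 × 2.24 = 0.45 UDE. The standard error of the mean change is 2/√30 = 0.37 at n=30 and 2/√150 = 0.16 at n=150 (the five procedures pooled, 5 × 30). Averaging the non-central t rejection probability over D gives these false-positive rates:

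| δ | n=30 | n=150 |
|---|---|---|
| 0 | 5% | 5% |
| 0.02 | 5.2% | 5.9% |
| 0.05 | 6.0% | 10.5% |
| 0.10 | 9.2% | 24.7% |
| 0.15 | 14.3% | 39.1% |
| 0.20 | 20.7% | 50.3% |
| 0.30 | 33.9% | 64.4% |

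Sensitivity for δ from 0.10 to 0.30:

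- K = 5: 7–22% at n=30 and 16–53% at n=150.
- SD of change 1.5, n=30: 12–45%. SD 3, n=30: 7–21%.
- Half the effect discounted because the event would have scored as unchecked anyway (δ from 0.05 to 0.15): 6–14% at n=30 and 10–39% at n=150.

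**4. What event-level recording could repair.** The Protocol collects other measures per event: "Data will be collected for specific events during the programmed driving scenario", and "The amount of rotation during each specified lane change or turning event during each testing interval will be collected and recorded". If UDE were also kept per event with its position, the analysis could weight front and rear equally. In a simulation of that analysis (4,000 runs, base UDE risk 0.10 per event, patient SD 0.7 on the logit scale, δ from 0.10 to 0.30) the false-positive rate returned to 4.5–5.4%.

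**5. What it could not repair.** Which position falls on which road event also changes with the visit. Suppose position counts are equal (5 front, 5 rear) but the front/rear difference varies between road events with an SD of 0.05, 0.10 or 0.15. False positives are then 6.0%, 9.2% and 14.2% at n=30, and 10.5%, 24.1% and 37.8% at n=150.

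**6. Aim 1.** Take true UDE rises of 1.0, 0.5 and 0 at 2, 6 and 12 weeks, K = 10 and SD of change 2. The probability that 2 weeks shows the largest observed decline is:

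| δ | n=30 | n=150 |
|---|---|---|
| 0 | 91.3% | 99.9% |
| 0.05 | 90.3% | 99.4% |
| 0.10 | 87.5% | 96.4% |
| 0.15 | 83.3% | 90.8% |
| 0.30 | 70.5% | 73.6% |

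At δ = 0.30 the fivefold larger sample gains almost nothing.

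**7. Check of the fix.** With equal position counts, a Williams order over four visits and a pairing SD of 0 to 0.15 (3,000 runs), false positives for pre-operative versus 2 weeks were 4.6–5.7% with layout as a fixed effect and 4.5–5.6% without it, at n = 20, 30 and 150.

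**The case against.** The strongest reply is that the sentence can be read otherwise. Elsewhere the Protocol uses the word trial for one patient's drive, so the second half could mean that each patient gets a fresh random layout after surgery. The three post-operative layouts would then be exchangeable, and the Aim 1 ranking problem would disappear. This is tenable, but the first half speaks of each phase and all patients, which makes one layout per visit the more natural reading. Even on the other reading the pre-operative layout is common to all, so contrasts with baseline stay affected: 7–22% false positives at n=30, K = 10 and δ from 0.10 to 0.30.

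Second, randomizing might mean shuffling a fixed set of positions. Counts would then be equal and only the pairing part (step 5) would remain. The Protocol does not say so.

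Third, a patient who cannot turn far enough to see a rear light may already score a UDE for not checking, whatever the layout. This is a fair point and could shrink the effect considerably. The halved δ range in step 3 allows for it, but the size of that discount is itself a guess.

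Fourth, no magnitude here comes from the document, and the n=150 column supposes a pooled test that the Protocol does not specify. That is correct. The confounding follows from the design; its size does not, and it is nil if the layouts are equally difficult.

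Finally, UDE is one of several performance measures and is not named primary. That limits the reach and is reflected in the verdict.

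**Conclusion.** The concern holds on the plain reading of the rule. Layout is fully confounded with visit in within-group contrasts of the UDE total, chiefly through the part scored for moving into an occupied spot. Both aims rest on such contrasts.

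The size is unknown. Under the assumptions in step 3, a single contrast at n=30 has a false-positive rate between about 5% (δ of 0.05 or less gives 5–6%) and 34% (δ = 0.30).

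The reach is limited to lane-change outcomes that depend on the layout. Collisions, centerline crossings, off-road excursions, reaction time, rotation measured before the drive, and differences in change between procedures are not directly affected. The unchecked part of UDE should depend much less on layout.

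The rule should be changed because the repair is cheap before data are collected and only partial afterwards. Confidence is medium, given the ambiguous wording and the assumed inputs.

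**What to change.** Replace the layout rule in section IV.N, Lane Changes and Blind Spot Detection, with text to this effect:

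> Layouts will be fixed before enrolment, each with the same number of occupied spots and equal numbers at L1, L2, R1 and R2. The order of four layouts over the pre-operative, 2-, 6- and 12-week visits will follow a 4×4 Latin (Williams) square within each repeatedly tested patient group. A fifth layout built to the same rule will be used at the optional 6-month visit. The four layouts will be rotated across controls, including their collar conditions. UDE will be recorded per event with its position, and layout will be a fixed effect in the analysis of lane-change outcomes.

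This puts 7 or 8 of 30 patients on each sequence in a surgical group, and 5 of 20 in the non-surgical myelopathy group if it is tested repeatedly. A patient who replaces a withdrawal takes over that sequence. Contrasts with the 6-month visit would rest on equal position counts alone; with the pairing variation of step 5 their simulated false-positive rate was 4.7–11.1% at n=30.

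If the order is not rotated, equal position counts at every visit are the minimum change. They remove the front/rear part and leave the pairing part.

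The cost is one paragraph, a sequence list, a position noted with each UDE, and slightly more operator set-up per visit. No patients, visits or equipment are added. No patient meets the same layout twice, so the protection against learning is kept.
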